#### CONFIDENTIAL

d=days, ETD=early treatment discontinuation (i.e. before the EoST/EoSA visit), ePRO=electronical patient-reported outcome, EoST/EoSA=end of study treatment/end of study assessments, N=nintedanib, P=pirfenidone.

The preferred sequence of study assessments is described in the CSP.

-  Only for subjects taking nintedanib at screening and randomization, until they stop taking nintedanib
-  For subjects not taking nintedanib at screening and randomization and those stopping nintedanib during the study
-  At these visits, the assessments from both the Every 12 weeks up to EoST/EoSA and the Every 24 weeks up to EoST/EoSA columns are included
- \* This can be a scheduled clinical study center visit or a phone call.

### 2.6. Sample Size Justification

See Section 7.1 of the clinical study protocols.

#### 2.7. Randomization and Blinding

Details on randomization and blinding are in Section 4.6 of the study protocols.

An independent data monitoring committee (IDMC) will monitor the safety of the subjects in the study on a regular basis and will also assess the effect of treatment with GLPG1690 on lung function as assessed by rate of decline in FVC to evaluate the risk-benefit. In addition, an interim analysis to assess futility will therefore be performed when a reasonable number of subjects have completed 52 weeks of treatment (e.g. at least 25% subjects from the two studies combined) (see Section 7.3.2 of the CSP). The results will be reviewed by the IDMC, who will then make a recommendation to the sponsor on the progress of the study. Specific details on timing of the analyses, futility criteria, and statistical analyses to be performed will be detailed in the IDMC charter or SAP, as appropriate. To allow collection of as much safety information as possible on a potential down-titration dose, a futile dose will continue if the other dose does not show futility. Either the study will continue as planned or both doses (and the study) will be terminated. Sponsor personnel will remain blinded and the study will not be stopped for a beneficial effect. The IDMC and statistical support group reporting to the IDMC will be unblinded, but they are independent of the study team. Sponsor personnel will remain blinded.

After it was decided to terminate the trial, part of the study team was unblinded in order to be able to investigate the findings.

# 3. ANALYSIS POPULATIONS

The analysis population will always be indicated in a subtitle in the table, listing or figure.

#### 3.1. All Screened Subjects Set

All enrolled subjects who underwent screening assessments to check whether or not they are eligible to participate in the clinical study.

#### 3.2. All Randomized Set

All enrolled subjects who underwent all screening assessments and were found to be eligible for the clinical study and who were randomized into the clinical study.

# 3.3. Full Analysis Set (FAS)

All randomized subjects who received at least one dose of IP.

All data will be included irrespective of IP interruption or termination and changes in standard of care. Only efficacy data after lung transplant will be excluded.

If a subject is unblinded (e.g. in case of a serious adverse event [SAE]), all data of this subject recorded in the database will be included in the analyses.

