#### For endpoints including vital status:

The last contact, including vital status information is defined as the latest date collected in the electronic case report form (eCRF) from the visit dates, AE dates, concomitant treatment dates, drug intake dates or laboratory test dates, study completion date or last contact or last known alive date from the vital status form.

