#### For endpoints not including vital status:

The last contact, not including mortality information is defined as the latest date collected in the eCRF from the date of death, visit dates, AE dates, concomitant treatment dates, drug intake dates or laboratory test dates, study completion date. Information from the vital status form is not to be taken into account for this calculation.

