# 9.3.2. Spirometry Parameters

All spirometry evaluations should be performed pre-bronchodilator. Spirometry data taken postbronchodilator will be excluded from the analysis.

The clinical study center-based spirometry must meet the criteria for acceptability and repeatability as defined in the American Thoracic Society / European Respiratory Society / Japanese Respiratory Society / Latin American Thoracic Association (ATS/ERS/JRS/ALAT) guidelines (Miller, et al., 2005) for screening, and will be based on ATS/ERS/JRS/ALAT guidelines after randomization.

Pulmonary function will be measured in a standardized manner and results should be transmitted electronically during the visit immediately after performing the spirometry and evaluated by a central reader. In case the acceptability and repeatability criteria as specified by ATS/ERS/JRS/ALAT guidelines are not met, a repeat spirometry should be performed during the same visit of the screening period. After randomization, a repeat spirometry should be performed during the same visit, based on the ATS/ERS/JRS/ALAT guidelines.

The data will be coded as "acceptable", "borderline acceptable" and "unacceptable", "unacceptable" values will be excluded from analyses.

The following parameters will be measured or calculated as part of the spirometry assessment:

- FVC (mL)
- Percent predicted FVC (%), as available in the database
- FEV1 (L) and percent predicted  $FEV_1(\%)$
- FEV1/FVC ratio
- FEF25-75 (mL/s).

The '2012 Global Lung Function Initiative Equations' will be used to calculate the predicted values (Ratitch B, 2013).

The spirometry endpoints will be analyzed using the FAS, including all available data before lung transplant for subjects who took at least one dose of IP, and excluding values post-bronchodilator.

For each of the spirometry parameters, descriptive statistics will be provided for the values, changes and percent change from baseline per time point up to the end of the study and per treatment group. Results will also be graphically displayed by means of line plots of the mean (SE) over time-by-treatment group.

A similar summary table and graph will also be provided by stratification factor (standard of care) and reason for not being on SOC.

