# 9.3.3. Second Key Secondary Endpoint - Time to First Respiratory-related Hospitalization until the end of the study

Respiratory hospitalizations will be adjudicated by the CEAC. The analysis will be based on the results from the adjudication, not on the investigator-reported information. Differences will be investigated and listed, if any.

The number (%) of subjects with an event during the study will be summarized as well as the number of events per 100 patients-years of follow-up. In addition, time to first event will be graphically displayed and tabulated (at each planned time point as described in Section 6.3, Week 2, Week 4, etc, and last available time point) using Kaplan-Meier estimates.

A Cox proportional hazards model with terms for age, sex, height, and stratum will be used to estimate the hazard ratios (and 95% CI) for each dose compared to placebo and to compare the active doses to placebo.

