#### Censoring

Time to event endpoints are defined from the date of first dose of IP.

If the subject did not have an event, the time to event will be censored at the last contact date, as defined in Section 6.5.

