# Censoring

Time to event endpoints are defined from the date of first dose of IP.

If the subject did not have an event, the time to event will be censored at the last contact date, as defined in Section 6.4.

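### Read literally, the SAP drops events after lung transplant but keeps the follow-up time; the exclusion should be limited to repeated measurements and the event and time rules matched

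*SAP*

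**What the plan says.** - **Exclusion.** SAP 3.3, on the full analysis set: "Only efficacy data after lung transplant will be excluded". It names no type of measurement.
- **What counts as efficacy.** Protocol 7.3.4 gives spirometry, clinical endpoints and quality of life as examples of efficacy parameters. Protocol 6.5.2 places mortality, hospitalization, transplant and exacerbation under efficacy assessments. SAP 9.3.3 and 9.3.3.1 sit under 9.3, Efficacy Analyses.
- **Censoring, second key secondary endpoint.** SAP 9.3.3: for a subject without an event, "the time to event will be censored at the last contact date, as defined in Section 6.5".
- **Last contact.** SAP 6.5 takes the latest of a list of dates. Without vital status the list runs "from the date of death, visit dates, AE dates, concomitant treatment dates, drug intake dates or laboratory test dates, study completion date"; with vital status it ends in "study completion date or last contact or last known alive date from the vital status form". Neither list mentions transplant.
- **Other time-to-event endpoints.** SAP 9.3.4: "censored at the last contact date, as defined in Section 6.4". Section 6.4 is the definition of baseline.
- **Use of follow-up time.** SAP 9.3.3 reports "the number of events per 100 patients-years of follow-up" beside Kaplan-Meier estimates and a Cox model.
- **Spirometry.** SAP 9.3.2 restates the exclusion for FVC and the other lung-function measures: "including all available data before lung transplant for subjects who took at least one dose of IP".

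**The concern.** An exclusion rule for outcomes and a censoring rule for follow-up have to refer to the same period. Here the first stops at transplant and the second does not. A subject transplanted without a prior event would stay in the risk set and in the patient-years denominator to last contact, but nothing that happened after transplant could count.

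The endpoints exposed are time to first respiratory-related hospitalization (the second key secondary), acute exacerbation, all-cause and respiratory-related mortality, and the composites that contain them. An all-cause mortality analysis that leaves out some deaths would not match its name. The first key secondary endpoint, disease progression to Week 52 (SAP 9.3.2.3), is touched as well: a death after transplant would go uncounted unless the FVC criterion had already been met.

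Transplant is a foreseeable event here. The note to exclusion criterion 17 in protocol 4.5.2 allows subjects on a transplant list. The list of reasons for stopping treatment in protocol 4.5.4 does not name transplant, and nothing ends study follow-up at that point, so contact dates after transplant are to be expected.

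**Working it through.** **1. Inputs.** The plan gives no transplant rate, hospitalization rate or event count, so it has no figure of its own on this point to reproduce. The power table in protocol 7.1 concerns FVC. From the documents: treatment lasts 52 to about 132 weeks per subject (protocol 4.1), with 250 subjects per arm. All rates below are assumptions.

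**2. Simple bound.** Let a share p of an arm be transplanted, event-free, at mid-follow-up. The literal rule keeps follow-up of 1 per subject; the matched rule keeps 1 − 0.5p. The literal rate is therefore the matched rate times (1 − 0.5p).

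- p = 1%: 1 − 0.5 × 0.01 = 0.995, an understatement of 0.5%.
- p = 3%: 1 − 0.5 × 0.03 = 0.985, an understatement of 1.5%.
- Ratio of the 1% arm to the 3% arm: 0.995 / 0.985 = 1.010. The other way round: 0.985 / 0.995 = 0.990.

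The arm with more transplants looks better by about 1%.

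**3. Exponential model.** Event hazard h, transplant hazard τ, s = h + τ, follow-up F uniform on 52 to 132 weeks (mean 92 weeks, 1.76 years). Per subject, averaged over F:

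- events before transplant: (h/s)(1 − e^(−sF))
- time to event, transplant or end: (1 − e^(−sF))/s
- time after transplant that the literal rule adds: τ[F/s − (1 − e^(−sF))/s²]

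Events divided by the second line return h. Events divided by the second plus third lines give the literal rate. With h = 0.12 per year (matched rate 12.00 per 100 patient-years):

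| τ per year | Transplanted before an event | Literal rate | Understated by |
|---|---|---|---|
| 0.005 | 0.8% | 11.94 | 0.5% |
| 0.01 | 1.6% | 11.88 | 1.0% |
| 0.02 | 3.1% | 11.77 | 1.9% |
| 0.04 | 6.1% | 11.55 | 3.8% |

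With h = 0.08 or 0.16 the understatement again runs from 0.5% to about 3.8%.

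**4. Effect on the comparison.** With a true hazard ratio of 1 and h = 0.12, the crude rate ratio (active to placebo), used here to approximate the Cox estimate, is:

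| τ active | τ placebo | Rate ratio |
|---|---|---|
| 0.01 | 0.01 | 1.000 |
| 0.01 | 0.02 | 1.010 |
| 0.005 | 0.02 | 1.015 |
| 0.01 | 0.04 | 1.029 |

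These figures compare the literal rule with stopping at transplant. They also apply to counting later events if the hazard is the same after transplant. If it is higher after transplant, the shortfall against counting those events is larger.

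**5. Disease progression to Week 52.** This is a proportion, so person-time does not enter. Each uncounted death moves an arm of 250 by 1/250 = 0.4 percentage points.

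**6. Whether the analyses are still planned.** For 9.3.3, the table of omitted analyses in SAP 9.1 removes only the on-treatment analysis and the negative binomial model. The Kaplan-Meier, Cox and patient-year analyses are not listed there, nor is 9.3.3.1.

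**The case against.** The best defence is that 3.3 was meant for lung function only. Wherever the SAP puts the exclusion into practice, it is for FVC: the primary estimand (Section 4), 9.3.2, the sensitivity analyses in 9.3.2.2 and Appendix 1. The time-to-event sections never mention it and say that results rest on adjudication. SAP 6.5 extends last contact to vital-status dates, and protocol 4.5.4 provides for vital status even from subjects who withdraw, which fits badly with discarding deaths. All this makes the narrow reading plausible as the intention. It does not settle the text: 3.3 carries no limit, the protocol's own use of the term efficacy includes clinical endpoints, and a separate statement in 9.3.2 would be unnecessary if 3.3 covered spirometry alone.

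Second, if post-transplant data are excluded, event-free time might be thought excluded too. That is a fair reading of 3.3 taken alone, but 6.5 fixes the end of follow-up explicitly and makes no exception.

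Third, the transplant admission may itself be the first hospitalization. This stands. All-cause hospitalization is largely unaffected if that admission counts as an event. For respiratory-related hospitalization it depends on how the adjudication committee classifies the admission, and its charter is not among the documents. The derivation details that SAP Section 1 places in a separate document are not available either.

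Fourth, little now turns on the result. The programme was stopped, pooled testing is cancelled, and the within-study hierarchy reaches the hospitalization endpoint only after the primary and first key secondary succeed. This limits the consequence. It does not remove the mismatch from analyses still to be reported.

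**Conclusion.** The point holds as a mismatch between two written rules. Applied literally, the SAP drops post-transplant deaths, exacerbations and respiratory hospitalizations while keeping the follow-up time, and leaves post-transplant deaths before Week 52 out of disease progression. No passage resolves this, and two programmers could build different datasets from the same text.

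The size is small: about 1% on the hazard ratio under an assumed 1% versus 3% imbalance in transplants, up to about 3% with a fourfold imbalance at the highest rate tried, and nil if transplant rates are equal (calculated at a true ratio of 1). Event rates within an arm would be understated by roughly 0.5% to 3.8% over the assumed range. The primary FVC analysis is unaffected.

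A reader might go further and infer that hazards will in fact be understated, or that any subject admitted some months after transplant will be shown as event-free to last contact. The documents do not support that. The SAP never states that adjudicated events after transplant are removed, the transplant admission may already be the event, and the comparison is distorted only if transplants differ between arms.

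**What to change.** - **SAP 3.3:** limit the exclusion to spirometry and other repeated measurements (DLCO, 6MWT, questionnaires). State that deaths after transplant count in all-cause mortality and in the mortality component of every composite, including disease progression to Week 52.
- **SAP 6.5 and 9.3.3 to 9.3.4:** for non-fatal event endpoints choose one matching rule: either count post-transplant events to last contact, or stop both events and person-time at the transplant date. Stopping at transplant can be informative, so treating transplant as a competing event is a reasonable alternative. Which to use is a choice; what matters is that events and time follow the same rule.
- **Composites:** say how the rule works for transplants outside the SAP's event wording. SAP 9.3.3.1 counts hospitalization for non-elective transplant, whereas the protocol endpoint is lung transplant.
- **SAP 9.3.4:** change the reference from Section 6.4 to Section 6.5.

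The cost is a few sentences in the SAP and a check of the derivation specifications. No new data are needed.

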# 3.4. Per Protocol (PP) Set

Per protocol analysis set is kept as documented in the original SAP for reference but will not be performed; nor will protocol deviations impacting the analysis be identified.

All randomized subjects who received at least one dose of IP, excluding subjects/data points with a major protocol violation which impacts the efficacy results. These protocol deviations are determined prior to unblinding and database lock for the final analysis and are entered in the database.

If a subject is unblinded (e.g. in case of an SAE), efficacy data will be disqualified from the per protocol analysis. Such data will still be included in the listings.

#### 3.5. Pharmacokinetic Analysis Set

All randomized subjects who received at least one dose of IP and for whom evaluable PK data were available (e.g. excluding protocol violations/deviations or AEs that may have an impact on the PK analysis).

# 4. PRIMARY ESTIMAND

International Council for Harmonisation (ICH) draft guidance E9(R1) "Statistical Principles for Clinical Trials: Addendum: Estimands and Sensitivity Analysis in Clinical Trials" specifies that a central question for drug development and licensing is to quantify treatment effects: how the outcome of treatment compares to what would have happened to the same subjects under different treatment conditions (e.g. had they not received the treatment or had they received a different treatment). Intercurrent events need to be considered in the description of a treatment effect on a variable of interest because both the value of the variable and the occurrence of the event may depend on treatment. The definition of a treatment effect, specified through an estimand, should consider whether values of the variable after an intercurrent event are relevant, as well as how to account for the (possibly treatment-related) occurrence or non-occurrence of the event itself. More formally, an estimand defines in detail what needs to be estimated to

address a specific scientific question of interest. A description of an estimand includes four attributes. The attributes in the CL-303 and CL-304 studies are underlined:

- A. the population, that is, the patients targeted by the scientific question: Patients with IPF, defined through appropriate inclusion/exclusion criteria to reflect the targeted patient population for approval:
- B. the variable (or endpoint), to be obtained for each patient, that is required to address the scientific question:

Rate of decline in FVC to Week 52;

C. the specification of how to account for intercurrent events to reflect the scientific question of interest:

The primary approach will include all data before lung transplant, irrespective of protocol violations, changes in SOC or IP interruptions or discontinuations.

Sensitivity analyses are planned to investigate the impact of the intercurrent events;

D. the population-level summary for the variable which provides, as required, a basis for a comparison between treatment conditions:

Difference in estimated slopes for each of the GLPG1690 doses versus placebo.

Together these attributes describe the estimand, defining the treatment effect of interest.

The design of the CL-303 and CL-304 studies targets this estimand as they are randomized parallel-group studies where every attempt is made to collect all measurements throughout the study.

# 5. TREATMENT GROUPS

# 5.1. Randomized Versus Actual Treatment

For efficacy, and safety analyses, the treatment group as assigned by the randomization will be used in the analysis (i.e. as-randomized analysis).

For PK analyses, the actual treatment will be used in the analyses.

Differences between as-treated and as-randomized will be flagged in the listing of subject randomization.

# 5.2. Totals over Groups

A total over all groups will be presented for the General and Baseline Characteristics part of the analysis, but not for efficacy, safety, PK nor analyses.

# 6. ANALYSIS PERIODS AND ANALYSIS TIME POINTS

# 6.1. Relative Number of Days

The timing of an assessment or an event relative to a reference date will be calculated as follows:

Relative day =concerned date-reference date +1 day,

when concerned date  $\geq$  reference date =concerned date-reference date, when the concerned date<reference date

- The reference date is the date of the first dose of IP administration, unless specified otherwise.
- The concerned date could be the measurement date of the assessment, or the start or end date of the event.
- *Date* implies a complete date having day, month and year available. Unless otherwise specified, the *relative day* will remain missing when it cannot be calculated due to absence or incompleteness of the concerned and/or reference dates.

### 6.2. Analysis Periods for Non-visit Data

These analysis periods are to be used for allocation of events into periods (e.g. adverse events).

Analysis period	Start period	End period
Screening	Date of signing the ICF.	1 day before the date of first dose of IP
Treatment	First dose of IP date.	Last dose of IP date + 30 days.
Follow-up	Last dose of IP date + 31 days.	Study termination date. Note: if the study termination date is before the last dose of IP + 30 days no follow-up period will be created.

Table 1Analyses Periods for Non-Visit Data

Note:

- If times are collected or other information with respect to timing (e.g. before or IP intake) this information will be taken into account in addition to the dates.
- The last analysis period in case of early termination will always end by the study termination date (date of last contact in the study or last known alive).

# 6.3. Algorithm of Allocating Visits to Time Analysis Windows

For the FAS analysis for efficacy, and safety endpoints, all data (including data obtained at unscheduled visits) will be placed into time analysis windows according to their relative day in the study, using to the following allocation tables (Table 2 to Table 4).

# Table 2Analysis Windows for Efficacy and Safety Endpoints Recorded at All Time
points (FAS and PP Approach)

Time point label	Target day	Interval lower bound	Interval upper bound
Baseline	1	-INF	1

Time point label	Target day	Interval lower bound	Interval upper bound
Week 2	15	2	21
Week 4	29	22	43
Week 8	57	44	71
Week 12	85	72	106
Week 18	127	107	154
Week 26	183	155	211
Week 34	239	212	267
Week 42	295	268	330
Week 52	365	331	407
Week 64	449	408	491
Week 76	533	492	575
Week 88	617	576	659
Week 100	701	660	743
Week 112	785	744	827
Week 124	869	828	911
Week 136	953	912	995
Etc.			

